**1. Personnel responsible for the safety review and its frequency:**

The principal investigator will be responsible for monitoring the data, assuring protocol compliance, and conducting the safety reviews at the specified frequency, which must be conducted at a minimum of every 6 months (including when reapproval of the protocol is sought). During the review process, the principal investigator will evaluate whether the study should continue unchanged, require modification/amendment, or close to enrollment. Either the principal investigator, or the IRB have the authority to stop or suspend the study or require modifications.

**2. The risks associated with the current study are deemed greater than minimal for the following reasons:** (choose those that apply)

1. We do not view the risks associated with the \_use of Ketorolac as minimal risks.

Although we have assessed the proposed study as one of greater than minimal risk, the potential exists for anticipated and/or unanticipated adverse events, serious or otherwise, to occur since it is not possible to predict with certainty the absolute risk in any given individual or in advance of first-hand experience with the proposed study methods. Therefore, we provide a plan for monitoring the data and safety of the proposed study as follows:

**3. Attribution of Adverse Events:**

Adverse events will be monitored for each subject participating in the study and attributed to the study procedures / design by the principal investigator *[name]* according to the following categories:

Possible: *bruising at place of injection, indigestion, allergic reaction, abdominal pain, abnormal bleeding, vomiting, diarrhea, constipation, gas, bloating, dizziness, drowsiness, sweating, nausea, ringing in the ears, & headaches* may be related to intraoperative Toradol use.

**4. Plan for Grading Adverse Events:**

The following scale will be used in grading the severity of adverse events noted during the study:

1. Mild adverse event- Abdominal pain (mild), headache, gas, bloating, indigestion, nausea
2. Moderate adverse event- Abdominal pain (mild), bruising at place of injection, sweating, diarrhea, dizziness, drowsiness, ringing in the ears
3. Severe- allergic reaction leading to anaphylaxis, abnormal bleeding

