9. **Risks:** Describe the reasonably foreseeable risks, including risks to subject privacy, discomforts, or inconveniences associated with subjects participating in the research.

*Additional risks from participating in this trial include those associated with the use of ketorolac. This includes but is not limited to bruising at place of injection, indigestion, allergic reactions including anaphylactic shock, abdominal pain, abnormal bleeding, vomiting, diarrhea, constipation, gas, bloating, dizziness, drowsiness, sweating, nausea, ringing in the ears, & headaches.*

The delivery of pain medications during ureteroscopy require the use of an intravenous (IV) line. This is a safe procedure used in every surgery requiring general anesthesia. There is a slight chance that multiple needle-sticks will be needed to make sure the IV is placed correctly. The subject might feel a small amount of pain when the IV is placed but it does not last very long. A bruise or a minor infection might develop where the IV is placed. A bruise will go away by itself and it might help if you wrap a warm towel around your arm. Infections can also be treated if necessary.

**10. Minimizing Risks:** Describe the manner in which the above-mentioned risks will be minimized.

*The above mentioned risks will be minimized as a thorough medication history for each patient will be assessed. Those who are previously known to have adverse events with NSAIDS or specifically ketorolac will be excluded. In addition, medication dosing will be in compliance with federal drug administration recommendation. For severe allergic reactions such as anaphylaxis, all patients will be under monitored anesthesia care during the procedure and immediately postoperatively and as such under the care of individuals trained to recognize and treat this. Patients who are older than 65 may be more sensitive to the effects of ketorolac and clear the drug more slowly, so for this population we will dose reduce to 15mg. In addition, abdominal pain, nausea, vomiting, hyperventilation, peptic ulcers and/or erosive gastritis and renal dysfunction which have been associated with single dose ketorolac have resolved with medication discontinuation and for the purposes of this study, participants will only receive one dose and subsequently be discontinued on it.*

A bruise from the IV will go away by itself and it might help to wrap a warm towel around the arm. Infections can also be treated with antibiotics if necessary.

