For the current study, the following individuals, funding, and/or regulatory agencies will be notified (choose those that apply):

- All Co-Investigators listed on the protocol.
- Yale Cancer Center Data and Safety Monitoring Committee (DSMC)
- National Institutes of Health
- Food and Drug Administration (Physician-Sponsored IND # \_\_\_\_\_)
- Medical Research Foundation (Grant \_\_\_\_\_)
- Study Sponsor
- Other Data Safety Monitoring Board (DSMB) or Committee (DSMC)

The principal investigator [name] will conduct a review of all adverse events upon completion of every study subject. The principal investigator will evaluate the frequency and severity of the adverse events and determine if modifications to the protocol or consent form are required.

- d. For multi-site studies for which the Yale PI serves as the lead investigator: This is a single site study
  - i. How will adverse events and unanticipated problems involving risks to subjects or others be reported, reviewed and managed?
  - ii. What provisions are in place for management of interim results?
  - iii. What will the multi-site process be for protocol modifications?

**12. Statistical Considerations:** Describe the statistical analyses that support the study design.

*All data will be collected prospectively. Preoperative data will include patient demographics, number of previous URS, baseline medications including analgesics, urine culture, stone size and location, and pain questionnaire scores. Mean scores will be calculated and compared between groups stratified by follow-up time. The number of adverse events and hospital admissions related to pain will recorded and described as counts and percentages. The primary outcome that will be used to estimate effect size is mean post-operative pain.*

*Our study is set up as two independent groups with a continuous outcome (Pain measured on a 1-10 scale) and an enrollment ratio of 1. We anticipate mean post-operative pain in the non-intervention group to be 7 with a standard deviation of 2. We aim to detect a 10% difference in pain, in the intervention arm. With an alpha of 0.05 and a power of 80% we will need to enroll 63 patients in each arm.*

SECTION VI: RESEARCH INVOLVING DRUGS, BIOLOGICS, RADIOTRACERS, PLACEBOS AND DEVICES
--

*If this section (or one of its parts, A or B) is not applicable, state N/A and delete the rest of the section.*

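### The adverse-event severity scale cannot be applied consistently: one entry sits in two grades, some named events have no grade or only a partial one, and the rest have a grade fixed by name

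*Combined protocol and SAP*

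**What the plan says.** Sub-item 4 of the Data and Safety Monitoring Plan (Section V, item 11) introduces its scale with "The following scale will be used in grading the severity of adverse events noted during the study". The scale consists of three lists:

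- "Mild adverse event- Abdominal pain (mild), headache, gas, bloating, indigestion, nausea"
- "Moderate adverse event- Abdominal pain (mild), bruising at place of injection, sweating, diarrhea, dizziness, drowsiness, ringing in the ears"
- "Severe- allergic reaction leading to anaphylaxis, abnormal bleeding"

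The three grades are not defined by intensity, effect on function or need for treatment, there or elsewhere in the document.

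Sub-item 3 (Attribution) names 16 events as possibly related to the study drug. They include the run "allergic reaction, abdominal pain, abnormal bleeding, vomiting, diarrhea, constipation, gas, bloating, dizziness, drowsiness, sweating, nausea", where abdominal pain and allergic reaction carry no qualifier. Section V, item 10 (Minimizing Risks) also refers to "peptic ulcers and/or erosive gastritis and renal dysfunction which have been associated with single dose ketorolac".

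Severity is then used. At the end of sub-item 7, the principal investigator "will evaluate the frequency and severity of the adverse events and determine if modifications to the protocol or consent form are required". Sub-item 6 allows the continuing-review summary to the IRB to state simply that events occurred at the expected frequency and severity. Section V, item 12 (Statistical Considerations) plans counts and percentages of adverse events, with no breakdown by grade.

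**The concern.** A severity scale should let two assessors give the same event the same grade, and should separate a trivial case from a bad one. This scale does neither. Two assessors who follow it to the letter can grade the same mild abdominal pain differently. For some events that the plan itself anticipates, there is no grade to give. For most of the others, the grade follows from the symptom's name and adds nothing to it.

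At stake is the quality of the severity information in the safety oversight of a study that the protocol rates as greater than minimal risk because of the study drug. The investigator's review and the IRB summary both refer to severity, and these grades are the only severity measure that the plan defines.

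**Working it through.** The plan states no figure to reproduce here. The check sets the 16 events in sub-item 3 against the three lists in sub-item 4, which have 6 mild, 7 moderate and 2 severe entries.

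| Result under sub-item 4 | Events from sub-item 3 | Number |
|---|---|---|
| Mild only | headache, gas, bloating, indigestion, nausea | 5 |
| Moderate only | injection-site bruising, sweating, diarrhea, dizziness, drowsiness, ringing in the ears | 6 |
| Severe only | abnormal bleeding | 1 |
| Both mild and moderate under the same label; no grade if worse than mild | abdominal pain | 1 |
| Graded only if it leads to anaphylaxis | allergic reaction | 1 |
| No grade | vomiting, constipation | 2 |

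**Total.** 5 + 6 + 1 + 1 + 1 + 2 = 16.

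**Not gradable uniquely or fully.** 1 + 1 + 2 = 4 of 16 (4/16 = 25%).

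**One fixed grade at any intensity.** 5 + 6 + 1 = 12 of 16 (12/16 = 75%). Any headache is mild, any sweating is moderate and any abnormal bleeding is severe.

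**Qualifiers.** Only abdominal pain and allergic reaction carry a qualifier, and neither yields a usable gradation. The abdominal-pain qualifier is identical in both grades, and the allergic-reaction qualifier admits one extreme only. So none of the 16 events can receive different grades at different intensities.

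**If the duplicate is a slip.** Suppose the second abdominal-pain entry was meant to say moderate. The duplicate goes, but severe abdominal pain still has no entry. Vomiting, constipation and non-anaphylactic allergic reaction stay ungraded, and the 12 fixed grades are unchanged. The count of 4 not fully gradable remains.

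**Comparison with item 10.** Hyperventilation, peptic ulcer, erosive gastritis and renal dysfunction are named there in connection with a single dose. None appears by name in sub-item 3 or sub-item 4. Gastrointestinal bleeding arguably falls under abnormal bleeding; renal dysfunction and a non-bleeding ulcer do not.

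**The case against.** The strongest reply is that little depends on the grade.

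- **No planned analysis uses it.** Item 12 plans overall counts and percentages only. This stands. A reader might infer that the trial's reported severity counts would be wrong, or that a comparison of severity between arms would be distorted, the more so because the surgical team is unblinded after surgery. The documents plan neither output, so they do not support that inference.
- **Other safeguards work without it.** Sub-item 5 judges seriousness separately, by outcome and medical judgment, and says that an event graded moderate may still be serious. Sub-item 6 sets its own three criteria for prompt reporting. Severity is one way for an event to be unexpected there, but the criterion is not tied to the grade lists. The research plan records all adverse drug reactions, so an ungraded event is still captured. This also stands. A reader might infer that the investigator could not decide on protocol or consent changes. That goes too far: the investigator reviews the events themselves after each subject completes, and the text does not confine that review to the grade labels.
- **The duplicate may be a typing slip.** This is plausible, but the documents do not show it, and correcting the word leaves the other defects.
- **The renal and ulcer point is weak.** A reader might infer that the plan overlooks these harms. It does not. Item 10 and the drug background in Section VI name them, the exclusion criteria cover renal insufficiency and peptic ulcer disease, and the attribution list is not said to be exhaustive. What remains is a secondary inconsistency between item 10 and the two monitoring-plan lists.

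These points limit the consequence. None of them supplies a grading rule that works.

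**Conclusion.** The concern holds as a defect in a stated rule, with limited reach. Followed as written, the scale fails to grade 4 of the 16 named events uniquely or fully, and it gives the other 12 a grade that carries no information on intensity. The severity grades available to the investigator's review and to the IRB summary would therefore be ambiguous (abdominal pain), incomplete (vomiting, constipation, non-anaphylactic allergic reaction) or uninformative (the rest).

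Total adverse-event counts, serious-event classification and the primary pain analysis are unaffected.

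The conclusion rests on two assumptions: that the three lists are the whole scale, as the introductory sentence implies, and that no separate grading instrument exists outside the documents. The correction should be made because it is cheap and severity is a named input to safety oversight. It does not call the efficacy results into question.

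**What to change.** Replace the event-name lists in sub-item 4 with definitions of mild, moderate and severe based on intensity, for example effect on usual activity and need for treatment. State that they apply to every recorded adverse event, listed or not. The named events can stay in sub-item 3 as a list of anticipated events without preassigned grades.

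Reconcile sub-items 3 and 4 with Section V, item 10. Either add peptic ulcer, erosive gastritis and renal dysfunction to the anticipated events, or state that the list is not exhaustive and that unlisted events are attributed and graded in the same way.

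The cost is one revised paragraph in the monitoring plan and a matching change to whatever form records adverse events. No visits, assessments or sample size change.

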**5. Plan for Determining Seriousness of Adverse Events:**

**Serious Adverse Events:**

In addition to grading the adverse event, the PI will determine whether the adverse event meets the criteria for a Serious Adverse Event (SAE). An adverse event is considered serious if it results in any of the following outcomes:

1. Death;

2. A life-threatening experience in-patient hospitalization or prolongation of existing hospitalization;
3. A persistent or significant disability or incapacity;
4. A congenital anomaly or birth defect; OR
5. Any other adverse event that, based upon appropriate medical judgment, may jeopardize the subject's health and may require medical or surgical intervention to prevent one of the other outcomes listed in this definition.

An adverse event may be graded as severe but still not meet the criteria for a Serious Adverse Event. Similarly, an adverse event may be graded as moderate but still meet the criteria for an SAE.

## **6. Plan for reporting UPIRSOs (including Adverse Events) to the IRB**

The principal investigator will report the following types of events to the IRB:

Any incident, experience or outcome that meets ALL 3 of the following criteria:

1. Is unexpected (in terms of nature, specificity, severity, or frequency) given (a) the research procedures described in the protocol-related documents, such as the IRB-approved protocol and informed consent document and (b) the characteristics of the subject population being studied; AND
2. Is related or possibly related to participation in the research (*possibly related* means there is a reasonable possibility that the incident, experience, or outcome may have been caused by the procedures involved in the research); AND
3. Suggests that the research places subjects or others at greater risk of harm (including physical, psychological, economic, legal, or social harm) than was previously known or recognized.

Unanticipated Problems Involving Risks to Subjects or Others (UPIRSOs) may be medical or non-medical in nature, and include – but are not limited to – *serious, unexpected, and related adverse events* and *unanticipated adverse device effects*. **Please note** that adverse events are reportable to the IRB as UPIRSOs **only** if they meet all 3 criteria listed above.

These UPIRSOs/SAEs will be reported to the IRB in accordance with IRB Policy 710, using the appropriate forms found on the website. All related events involving risk but not meeting the *prompt* reporting requirements described in IRB Policy 710 should be reported to the IRB in summary form at the time of continuing review. If appropriate, such summary may be a simple brief statement that events have occurred at the expected frequency and level of severity as previously documented. In lieu of a summary of external events, a current DSMB report can be submitted for research studies that are subject to oversight by a DSMB (or other monitoring entity that is monitoring the study on behalf of an industry sponsor).

**7. Plan for reporting adverse events to co-investigators on the study, as appropriate the protocol's research monitor(s), e.g., industrial sponsor, Yale Cancer Center Data and Safety Monitoring Committee (DSMC), Protocol Review Committee (PRC), DSMBs, study sponsors, funding and regulatory agencies, and regulatory and decision-making bodies.**

For the current study, the following individuals, funding, and/or regulatory agencies will be notified (choose those that apply):

- All Co-Investigators listed on the protocol.
- Yale Cancer Center Data and Safety Monitoring Committee (DSMC)
- National Institutes of Health
- Food and Drug Administration (Physician-Sponsored IND # \_\_\_\_\_)
- Medical Research Foundation (Grant \_\_\_\_\_)
- Study Sponsor
- Other Data Safety Monitoring Board (DSMB) or Committee (DSMC)

The principal investigator [name] will conduct a review of all adverse events upon completion of every study subject. The principal investigator will evaluate the frequency and severity of the adverse events and determine if modifications to the protocol or consent form are required.

- d. For multi-site studies for which the Yale PI serves as the lead investigator: This is a single site study
  - i. How will adverse events and unanticipated problems involving risks to subjects or others be reported, reviewed and managed?
  - ii. What provisions are in place for management of interim results?
  - iii. What will the multi-site process be for protocol modifications?

**12. Statistical Considerations:** Describe the statistical analyses that support the study design.

*All data will be collected prospectively. Preoperative data will include patient demographics, number of previous URS, baseline medications including analgesics, urine culture, stone size and location, and pain questionnaire scores. Mean scores will be calculated and compared between groups stratified by follow-up time. The number of adverse events and hospital admissions related to pain will recorded and described as counts and percentages. The primary outcome that will be used to estimate effect size is mean post-operative pain.*

*Our study is set up as two independent groups with a continuous outcome (Pain measured on a 1-10 scale) and an enrollment ratio of 1. We anticipate mean post-operative pain in the non-intervention group to be 7 with a standard deviation of 2. We aim to detect a 10% difference in pain, in the intervention arm. With an alpha of 0.05 and a power of 80% we will need to enroll 63 patients in each arm.*

SECTION VI: RESEARCH INVOLVING DRUGS, BIOLOGICS, RADIOTRACERS, PLACEBOS AND DEVICES
--

*If this section (or one of its parts, A or B) is not applicable, state N/A and delete the rest of the section.*

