Following the procedure, patients will rate their pain using a visual pain assessment scale at 1 hour postoperatively and at the time of discharge from the recovery room. Once the patient is at home, they will fill out a validated survey that has questions related to pain. This will be filled out once a day for a total of 7 days following the procedure. In addition, we will provide a medication utilization diary sheet for the patient to record daily use of prescribed narcotic and other as needed over the counter medications such as acetaminophen and ibuprofen. This will also be done daily for a total of 7 days. The patient will be surveyed at their one-week postoperative visit using the same assessment. All adverse drug reactions will be recorded from time of administration to initial follow-up. The following is the study schedule:

Study Schedule	Preop	Intraop	1hr post op	2 hr post op	1 week
Assessments					
Consent	x				
History and Physical	x				
Urine Culture					
Post URS medication record			x	x	
Pain Questionnaire	x		x	x	x
Adverse Events		x	x	x	x

4. Genetic Testing N/A

A. Describe

- i. the types of future research to be conducted using the materials, specifying if immortalization of cell lines, whole exome or genome sequencing, genome wide association studies, or animal studies are planned
- ii. the plan for the collection of material or the conditions under which material will be received
- iii. the types of information about the donor/individual contributors that will be entered into a database
- iv. the methods to uphold confidentiality

B. What are the conditions or procedures for sharing of materials and/or distributing for future research projects?

C. Is widespread sharing of materials planned?

D. When and under what conditions will materials be stripped of all identifiers?

E. Can donor-subjects withdraw their materials at any time, and/or withdraw the identifiers that connect them to their materials?

- i. How will requests to withdraw materials be handled (e.g., material no longer identified: that is, anonymized) or material destroyed)?

F. Describe the provisions for protection of participant privacy

G. Describe the methods for the security of storage and sharing of materials

5. **Subject Population:** Provide a detailed description of the types of human subjects who will be recruited into this study.

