*Only patients with the following indications for URS will be included: All patients who are undergoing elective ureteroscopy for management of stone disease without contraindication to ketorolac.*

6. **Subject classification:** Check off all classifications of subjects that will be specifically recruited for enrollment in the research project. Will subjects who may require additional safeguards or other considerations be enrolled in the study? If so, identify the population of subjects requiring special safeguards and provide a justification for their involvement.

- |  |  |  |
|--|--|--|
|  Children              |  Healthy                |  Fetal material, placenta, or dead fetus |
|  Non-English Speaking  |  Prisoners                         |  Economically disadvantaged persons      |
|  Decisionally Impaired |  Employees                         |  Pregnant women and/or fetuses           |
|  Yale Students         |  Females of childbearing potential |  |

NOTE: Is this research proposal designed to enroll children who are wards of the state as potential subjects?  Yes  No (If yes, see Instructions section VII #4 for further requirements)

7. **Inclusion/Exclusion Criteria:** What are the criteria used to determine subject inclusion or exclusion?

*Inclusion criteria*

*Kidney Stones requiring surgery  
Ureteral stones requiring surgery  
Able to undergo general anesthetic  
Willing and able to consent to treatment  
Willing and able to complete all questionnaires  
18 years of age and older*

*Exclusion criteria*

*Solitary Kidney  
Anatomic Bladder or ureteral abnormality  
Previous urinary diversion  
Interstitial cystitis  
Pregnancy  
Ectopic kidney  
Renal failure  
Coagulopathy  
Neurogenic bladder  
Transplanted kidney  
Indwelling foley catheter or suprapubic tube  
Chronic narcotic use  
Known contraindications to agent (NSAID allergy, renal insufficiency, NSAID induced asthma, peptic ulcer disease, bleeding diathesis, pregnancy/breast feeding, or advanced age)*

8. How will **eligibility** be determined, and by whom?

*Eligibility will be determined based on URS indications and inclusion and exclusion criteria. All patients will be determined eligible by [name]*

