**Choose one:**

- For entire study
- For recruitment purposes only
- For inclusion of non-English speaking subject if short form is being used

- i. Describe why it would be impracticable to obtain the subject's authorization for use/disclosure of this data;
- ii. If requesting a waiver of **signed** authorization, describe why it would be impracticable to obtain the subject's signed authorization for use/disclosure of this data;

**By signing this protocol application, the investigator assures that the protected health information for which a Waiver of Authorization has been requested will not be reused or disclosed to any person or entity other than those listed in this application, except as required by law, for authorized oversight of this research study, or as specifically approved for use in another study by an IRB.**

*Researchers are reminded that unauthorized disclosures of PHI to individuals outside of the Yale HIPAA-Covered entity must be accounted for in the "accounting for disclosures log", by subject name, purpose, date, recipients, and a description of information provided. Logs are to be forwarded to the Deputy HIPAA Privacy Officer.*

- 7. Required HIPAA Authorization:** If the research involves the creation, use or disclosure of protected health information (PHI), separate subject authorization is required under the HIPAA Privacy Rule. Indicate which of the following forms are being provided:

- Compound Consent and Authorization form
- HIPAA Research Authorization Form

- 8. Consent Personnel:** List the names of all members of the research team who will be obtaining consent/assent.

*[name] will be obtaining consent/assent*

- 9. Process of Consent/Assent:** Describe the setting and conditions under which consent/assent will be obtained, including parental permission or surrogate permission and the steps taken to ensure subjects' independent decision-making.

*The PI routinely consults with patients regarding urinary stones. During the initial outpatient consultation with the PI, patients who are candidates for ureterscopic management and are in agreement to this surgical method will be recruited to participate in the study. These are all patients being seen in the outpatient clinic prior to surgery and are not under any acute distress/pain.*

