*The investigator will explain the research study to the participant and answer any questions that may arise. The participants will sign the informed consent document prior to any procedures being done specifically for the study. The participants will have sufficient opportunity to discuss the study and process the information in the consent process prior to agreeing to participate. A copy of the informed consent document will be given to the participants for their records. The rights and welfare of the participants will be protected by emphasizing to them that the quality of their medical care will not be adversely affected if they decline to participate in this study. The acquisition of informed consent will be documented in the participant's medical records. The informed consent form will be signed and personally dated by the participant and the person who conducted the informed consent discussion. The original signed informed consent form will be retained in the medical chart and a copy will be provided to the participant*

- 10. Evaluation of Subject(s) Capacity to Provide Informed Consent/Assent:** Indicate how the personnel obtaining consent will assess the potential subject's ability and capacity to consent to the research being proposed.

*The PI performs a mental status exam as part of every physical exam during clinic visit. This exam assesses the subjects thought process, cognition, insight, and judgement. In addition to using this routine exam, the PI will assess the subject's ability and capacity to consent by asking questions during the consent process to gauge whether they have an understanding of the study. If the subject does not fully understand the study as it is described, he/she will not be enrolled.*

- 11. Documentation of Consent/Assent:** Consent form and pain assessment questionnaire will be used during the consent/assent process. Copies are attached

- 12. Non-English Speaking Subjects:** Explain provisions in place to ensure comprehension for research involving non-English speaking subjects. If enrollment of these subjects is anticipated, translated copies of all consent materials must be submitted for approval prior to use.

*We will not be recruiting non-English speaking patients in this trial.*

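### Optional gain, not an error: the pre-operative pain score is already collected and could serve as an ANCOVA covariate

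*Combined protocol and SAP*

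**What the plan says.** The pre-operative score is collected. Section V, item 12 states: "Preoperative data will include patient demographics, number of previous URS, baseline medications including analgesics, urine culture, stone size and location, and pain questionnaire scores". The Study Schedule in Section V, item 3 marks the "Pain Questionnaire" row in the Preop column as well as at 1 hour, 2 hours and 1 week. Section VII, item 11 adds: "Consent form and pain assessment questionnaire will be used during the consent/assent process. Copies are attached".

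The analysis of pain is a single sentence in Section V, item 12: "Mean scores will be calculated and compared between groups stratified by follow-up time". The sample-size paragraph that follows begins "Our study is set up as two independent groups with a continuous outcome" and uses a control mean of 7, SD 2, a 10% difference, alpha 0.05, 80% power and 63 patients per arm. No model, covariate or change score is named anywhere, and no section gives the pre-operative pain score a stated role in the treatment comparison.

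Three other statements bear on how useful that score would be. On patients at the consent visit, Section VII, item 9 says: "These are all patients being seen in the outpatient clinic prior to surgery and are not under any acute distress/pain". Section V, item 7 excludes "Chronic narcotic use" and requires patients to be "Willing and able to complete all questionnaires".

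**The concern.** The issue is efficiency, not bias. Randomisation makes the unadjusted difference in means a fair estimate. The pre-operative score is taken before the drug is given, so treatment cannot affect it, and adjusting for it leaves the target mean difference unchanged. If the score predicts post-operative pain, adjustment shrinks the residual variance by the factor 1 − r² and narrows the confidence interval at almost no cost.

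Extra precision would be useful. The enrolment target of 126 is exactly 2 × 63, with no allowance for dropout.

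There is a smaller side benefit. The baseline score will be in the dataset with no rule for its use, so naming one analysis in advance closes the choice between adjusted and unadjusted results.

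**Working it through.** **Inputs from Section V, item 12:** SD 2, 63 per arm, alpha 0.05, power 80%, 10% difference. Sidedness is not stated; I take two-sided. **Assumed:** r from 0 to 0.5, because the documents give no value.

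**1. The plan's own figure.** Normal approximation: n per arm = 2 × [SD × (1.960 + 0.842) / δ]².
- δ = 1.0 (10% of a 10-point scale): 62.8, rounded up to 63. This reproduces the plan.
- δ = 0.7 (10% of the mean of 7): 128.1, rounded up to 129. This does not.

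The plan's 63 therefore corresponds to a 1.0-point difference. I show both readings.

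**2. Unadjusted analysis.** SE = 2 × √(2/63) = 0.356, with 124 df. By the noncentral t, power is 79.5% at 1.0 point and 49.6% at 0.7. The 95% CI half-width is 1.979 × 0.356 = 0.705.

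**3. ANCOVA.** SE = 2 × √(1 − r²) × √(2/63) × √(1 + 1/122), with 123 df. The last factor, with 122 = 2 × 63 − 4, is the cost of estimating the slope. For r = 0.3: 2 × 0.954 × 0.1782 × 1.0041 = 0.341.

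| r (assumed) | Power at 1.0 | Power at 0.7 | CI half-width | Equivalent unadjusted n per arm |
|---|---|---|---|---|
| Unadjusted | 79.5% | 49.6% | 0.705 | 63 |
| 0 | 79.2% | 49.3% | 0.708 | 62.5 |
| 0.1 | 79.6% | 49.6% | 0.705 | 63.1 |
| 0.2 | 80.8% | 50.8% | 0.694 | 65.1 |
| 0.3 | 82.8% | 53.0% | 0.676 | 68.6 |
| 0.5 | 89.3% | 61.1% | 0.613 | 83.0 |

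Break-even is at r of about 0.09. At 0.7 points, 80% power would need r of about 0.72. In simulation (100,000 trials per value of r), ANCOVA power agreed with the table and type I error was 4.95% to 5.03%.

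**4. Missing baseline scores.** Suppose about 10% are missing (an assumption).
- Dropping those patients leaves 57 per arm. Power at 1.0 point is then 75.0% at r = 0 and 78.9% at r = 0.3, below the unadjusted 79.5% unless r exceeds about 0.32.
- Filling each missing score with the mean over both arms keeps all 63. Simulated power is 79.3% at r = 0 and 82.5% at r = 0.3, with type I error of 4.9% to 5.0%.

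**5. Leaving the choice open.** If both analyses were run and the more favourable one reported, simulated type I error would be 5.3% (r = 0), 6.4% (r = 0.3) or 7.3% (r = 0.5) instead of 5%.

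**The case against.** The strongest counter-argument is that the gain is small where r most plausibly lies. Patients recruited without acute pain, with chronic narcotic users excluded, may have baseline scores bunched near the floor. At r of 0.1 to 0.3 the gain is 0.1 to 3.3 percentage points of power, and below about 0.09 there is a slight loss. The r = 0.5 figures have no support in the documents. This stands, and it is why the point is optional. It is not certain, though: the Preop column carries no date, and a form completed nearer to surgery might behave differently.

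A second objection is practical. Section VIII says the questionnaires carry no identifying information, whereas ANCOVA must link each patient's pre- and post-operative scores. That does not block the change. A participant code is not ruled out, and one is needed in any case to assign home questionnaires to an arm and a day. The linkage should still be written down.

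Third, the attached questionnaire is not available to this review, so whether it yields one numeric score is unknown. The covariate need not share the outcome's 1-10 scale, but the plan should say which score is meant.

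Finally, fixing adjusted versus unadjusted leaves a larger freedom open, because no primary time point is named. That is correct, so the side benefit is minor. Nor does the requirement to be able to complete questionnaires guarantee that every baseline form is filled in.

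**Conclusion.** The point holds as an optional improvement; the plan contains no error here. Under the reading that reproduces 63 per arm, adjustment changes power by −0.3 percentage points at r = 0, +1.3 at r = 0.2 and +3.3 at r = 0.3. The figure is +9.8 at r = 0.5, which is less plausible in this population. These results rest on SD 2, full enrolment, a two-sided test and an assumed r.

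The gain should be taken as precision and not used to reduce enrolment. Adjustment does not settle what a 10% difference means or which time point is primary; both are separate matters.

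**What to change.** Before outcome data are analysed, replace the comparison sentence in Section V, item 12 with:

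> Post-operative pain at each follow-up time will be compared between arms by ANCOVA with the pre-operative pain questionnaire score as covariate, reporting the adjusted mean difference with its 95% CI. The unadjusted difference will be a sensitivity analysis. A missing pre-operative score will be set to the mean of all available pre-operative scores, both arms pooled.

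If the questionnaire gives more than one score, name the one to be used. State in Section VIII that forms carry a participant code, so that pre- and post-operative scores can be linked.

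The cost is a few sentences of plan text and one degree of freedom, at worst about 0.3 percentage points of power. No patients, visits or assessments are added, and the number of follow-up comparisons is unchanged.
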